Dose escalation will be paused until further evaluation by the DMC if any of the following criteria are met. If it is confirmed that a stopping criterion was met, no further dosing will take place until after submission and approval of a substantial amendment if the DMC recommends the trial can continue.

- One or more participants experiencing at least possibly related Common Terminology Criteria for Adverse Events (CTCAE) Grade ≥ 3 TEAE or CTCAE grade ≥ 3 laboratory abnormality in a single cohort.
 - All grade 3 toxicities for vital signs must be confirmed with a repeat measurement obtained within 1 hour.
 - All grade 3 toxicities for laboratory parameters must be confirmed with a repeat measurement obtained within 24 hours.
- Two or more participants experiencing at least possibly related CTCAE grade ≥ 2 TEAEs or CTCAE Grade ≥ 2 laboratory abnormalities in a single cohort.
 - All grade 2 toxicities for vital signs must be confirmed with a repeat measurement obtained within 1 hour.
 - All grade 2 toxicities for laboratory parameters must be confirmed with a repeat measurement obtained within 24 hours.
- One or more participants experiencing any at least possibly related SAE in a single cohort.

Period 2 Individual Stopping Criteria:

Dosing will be paused or discontinued (per Investigator judgment) for an individual participant at any time in the study if:

- Participant experiences any severe or serious adverse event considered at least possibly related to study drug.
- Participant experiences, in the Investigator's opinion, clinically significant hypersensitivity to WVE-006 (or placebo) administration.
- Participant has any medical condition that is judged by the Investigator to jeopardize the participant's safety if he or she continues to receive the study drug.

On discontinuation of treatment, participants will be encouraged to continue follow-up for safety per protocol. Per Investigator judgment with consultation with the Sponsor, the participant may be allowed to resume participation in the study if/when the event has resolved.

Sponsor: Wave Life Sciences UK Limited	Investigational Product: WVE-006	Developmental Phase: Phase 1	IRAS ID Number: 1008635

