4 STUDY DESIGN

4.1 Overall Study Design

This is a double-blind, placebo-controlled, single ascending dose (SAD) and multidose Phase 1 study to assess the safety, tolerability, and PK of WVE-006 in healthy participants. Participants will be randomized to WVE-006 or placebo.

Period 1 will evaluate single ascending doses of WVE-006 in up to five cohorts of up to 8 healthy participants each (3:1 active:placebo). An additional cohort (Cohort 6) may be included to evaluate concentration-QTc. Participants may be on-study for up to 12 weeks. A sentinel strategy will be employed for the first 2 participants (1 active:1 placebo) of every new dose level during the SAD portion (Period 1) and in the multiple dose portion (Period 2) of the study, with a 48-hour observation period to assess for acute safety events. The Dose Escalation Committee (DEC) and the DMC will review available data through Day 8 that will include key PK parameters and safety for each dose cohort, as well as previously accumulated safety data and available PK data, to recommend subsequent dose escalation. Additional details are provided in [Section 4.1.2](#).

Dose Escalation Stopping Criteria (Period 1):

Dose escalation will be paused until further evaluation by the DMC if any of the following criteria are met. If it is confirmed that a stopping criterion was met, no further dosing will take place until after submission and approval of a substantial amendment if the DMC recommends the trial can continue.

- One or more at least possibly related Common Terminology Criteria for Adverse Events (CTCAE) Grade ≥ 3 TEAE or CTCAE grade ≥ 3 laboratory abnormality in a single cohort.
 - All grade 3 toxicities for vital signs must be confirmed with a repeat measurement obtained within 1 hour.
 - All grade 3 toxicities for laboratory parameters must be confirmed with a repeat measurement obtained within 24 hours.
- Two or more at least possibly related CTCAE grade ≥ 2 TEAEs or CTCAE Grade ≥ 2 laboratory abnormalities in a single cohort.
 - All grade 2 toxicities for vital signs must be confirmed with a repeat measurement obtained within 1 hour.
 - All grade 2 toxicities for laboratory parameters must be confirmed with a repeat measurement obtained within 24 hours.
- Any at least possibly related SAE in a single cohort.

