- A treatment-emergent AE (TEAE) is defined as an AE not present before exposure to study treatment or any event already present that worsens in severity or frequency from the date of receiving first dose of study treatment to study completion or discontinuation.

General rules of analysis and reporting of AEs:

- AEs reported by Investigators will be coded to system organ class (SOC) and preferred term (PT) using the Medical Dictionary for Regulatory Activities (MedDRA).
 - For an event with multiple occurrences during the study, the event is only counted once in occurrence summary, the maximum severity is used when reporting the severity, the highest level of association will be used to characterize relatedness to study drug in reporting.
-

The number and percentage of participants who have at least a TEAE, a grade 3 or 4 TEAE, a study drug-related TEAE as judged by the Investigator will be summarized by dose group. In addition, the number and percentage of participants who have a TEAE that leads to study drug discontinuation or who died due to occurrence of a TEAE will also be summarized by dose group. The percentage for the aforementioned summaries will be calculated based on the number of participants in each dose group.

For each dose group, TEAEs will be presented by PT with the descending frequency of occurrence based on the pooled WVE-006 dose groups. In addition, TEAEs will also be summarized by SOC, PT, and the severity for each dose group.

The number and percentage of participants who had at least one SAE will be summarized by SOC and PT for each dose group. In addition, SAEs will be tabulated by dose group.

9.3.5.2 *Analysis of Clinical Laboratory Evaluations, Vital Signs, and ECG Parameters*

For laboratory parameters, change from baseline to maximum or minimum value during the study will be summarized by dose group for each parameter and reported by laboratory group, respectively. In addition, changes from baseline to each post-baseline visit will also be summarized by dose group.

Clinically significant changes will be summarized by dose group for vital signs.

A shift table presenting the shift from baseline to each post-baseline assessment in terms of Normal or Abnormal by dose group will be used to report ECG findings during the study.

9.3.6 *Pharmacokinetic Analysis*

PK data will be summarized descriptively and presented in both graphical and/or tabular formats.

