10.2 Appendix 2: Clinical Laboratory Tests

- The tests detailed in [Table 11](#) will be performed per the Sponsor provided Laboratory Manual.
- Laboratory tests will be done at the time points per the SoA in [Section 1.3](#). Urine dipstick and urine pregnancy test results will be recorded in the participant's medical record and corresponding eCRFs.
- Protocol-specific laboratory value requirements for inclusion or exclusion of participants are detailed in [Section 5](#) of the protocol.
- Additional tests may be performed at any time during the study as determined necessary by the Investigator or required by local regulations.
- Investigators must document their review of each laboratory safety report. Any laboratory result considered by the Investigator as clinically significant must be documented as AE and graded per CTCAE criteria. (see [Section 10.3](#)).

Table 11 Detailed Clinical Laboratory Tests

Laboratory Tests	Parameters	
Hematology¹	
 • Platelet count 	
	
 • Red blood cell (RBC) count 	
	
 – RBC indices 	
 – Mean corpuscular volume (MCV) – Mean corpuscular hemoglobin (MCH) – Mean corpuscular hemoglobin concentration (MCHC) – %Reticulocytes
	
 • White blood cell (WBC) count with differential: 	
 – Neutrophils – Lymphocytes – Monocytes – Eosinophils – Basophils
	
 • Hemoglobin • Hematocrit 	
	
 • Markers of Inflammation 	
 – C-reactive protein – Complement (C3, Bb, C3a, and sC5b9)
Clinical chemistry²	
 • Blood urea nitrogen (BUN) • Potassium • Creatinine • Sodium • Gamma glutamyl transferase • Chloride • Bicarbonate • Blood glucose 	
 • Aspartate transaminase (AST) • Alanine transaminase (ALT) • Alkaline phosphatase • Total Bilirubin (direct bilirubin if Total Bilirubin is elevated) • Creatine phosphokinase • Total protein • Albumin¹ • Glutamate dehydrogenase (GLDH)

Coagulation¹	
 • Prothrombin time or international normalized ratio (INR) (per site's laboratory standards) • Activated partial thromboplastin time (aPTT) • Fibrinogen

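### The laboratory analysis in Section 9.3.5.2 plans no count of participants by CTCAE grade, and the passages on which laboratory results are graded and counted need reconciling

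*Combined protocol and SAP*

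**What the plan says.** **Endpoint.** Section 3 (Table 8) includes changes in clinical laboratory results in the primary endpoint.

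**Laboratory analysis.** Section 9.3.5.2 states: "For laboratory parameters, change from baseline to maximum or minimum value during the study will be summarized by dose group". It adds that "changes from baseline to each post-baseline visit will also be summarized by dose group". It names no table, shift or listing by grade. The same section gives vital signs a summary of clinically significant changes and ECGs a normal/abnormal shift from baseline.

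**AE analysis.** Section 9.3.5.1 counts participants with a grade 3 or 4 TEAE and summarises TEAEs by SOC, PT and severity.

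**Grading instruction.** Section 10.2 (Appendix 2) says: "Any laboratory result considered by the Investigator as clinically significant must be documented as AE and graded per CTCAE criteria".

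**Stopping criteria.** The Period 1 criteria list laboratory abnormalities as an alternative to TEAEs at grade 2 or higher and at grade 3 or higher; in Section 4.1 the grade 2 item ends with "laboratory abnormalities in a single cohort". Both the synopsis (Section 1.1) and Section 4.1 require confirmation; for grade 2, "All grade 2 toxicities for laboratory parameters must be confirmed with a repeat measurement obtained within 24 hours", with a matching line for grade 3. The synopsis counts people: "Two or more participants experiencing at least possibly related CTCAE grade" and "One or more participants experiencing at least possibly related Common Terminology Criteria for Adverse Events (CTCAE) Grade". Section 4.1 does not: "Two or more at least possibly related CTCAE grade".

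**The concern.** The plan treats the CTCAE grade of a laboratory value as informative enough to pause dose escalation and to define the MTD (Section 4.1.2), but the analysis of the same data does not use grade. A summary of change describes the average shift and its extremes. It does not say how many participants crossed a limit, and in cohorts this small that is what a safety reader most needs.

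If a grade 2 or higher value is not called clinically significant, it is not recorded as an AE, and so it is missing from the severity tables too. The report could then describe mean changes in each analyte without saying how often graded abnormalities occurred on each dose or on placebo.

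**Working it through.** The plan gives no figure to reproduce: Section 9.1 says the sample size was not based on hypothesis testing, and no abnormality rates are stated. The check is mainly a comparison of texts, with some simple arithmetic.

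**Step 1. Where each kind of laboratory result is counted.**

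| Laboratory result | Change summaries (9.3.5.2) | TEAE tables (9.3.5.1) | Participant count by grade |
|---|---|---|---|
| Treatment-emergent, called clinically significant | yes | yes, with severity | through the TEAE tables only |
| Grade 2 or higher, not called clinically significant | yes | no | none planned |

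**Step 2. What the change summaries can show.** Section 9.3.1 gives n, mean, SD, median, minimum and maximum. The largest change in a group comes from one participant. If a second participant also reaches grade 2 but with a smaller change, the maximum does not move. The mean, SD and median do move, but they do not reveal how many participants crossed a limit.

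**Step 3. Size of the distinction.**
- Full active group of 6: 1/6 = 16.7%; 2/6 = 33.3%.
- Full cohort of 8, the unit named in the stopping criteria: 1/8 = 12.5%; 2/8 = 25.0%.
- Pooled Period 1 placebo: 5 cohorts × 2 = up to 10 participants, or 6 × 2 = 12 with the optional cohort. This is the comparator that a count by grade would make usable.

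**Step 4. Which results are graded.** Section 10.2 attaches the duty to grade to clinically significant results. The synopsis and Section 4.1 require all grade 2 and grade 3 laboratory toxicities to be confirmed within 24 hours, which presupposes grading without that condition. No passage says who grades the remaining values, or how.

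**Step 5. What is counted.** At the grade 3 threshold of one, counting participants or events gives the same answer. At the grade 2 threshold of two it does not: one participant with two qualifying abnormalities meets the wording of Section 4.1 but not that of the synopsis.

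**Step 6. How much the reading in step 4 could matter (illustration only).** Let p be the chance that a participant has a qualifying grade 2 or higher laboratory abnormality, and f the fraction of these that are graded. Both are assumed. With independent participants and a cohort of n = 8, let q = pf. Then P(at least 2 counted) = 1 − (1 − q)^8 − 8q(1 − q)^7.

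| p | f = 1 | f = 0.5 | Ratio |
|---|---|---|---|
| 0.05 | 0.057 | 0.016 | 3.6 |
| 0.10 | 0.187 | 0.057 | 3.3 |
| 0.20 | 0.497 | 0.187 | 2.7 |

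The two readings can therefore lead to quite different behaviour of the rule. The table does not show that any value would in fact go ungraded.

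**The case against.** Much of the opposing case stands, and it rules out several stronger conclusions that a reader might draw.

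- **That laboratory values are graded only if clinically significant.** Section 10.2 does not say only, and the confirmation requirement points to wider grading. The texts are inconsistent; they do not establish a restriction.
- **That the count is never produced, so escalation proceeds without it.** Escalation rests on DEC and DMC review, not on the final analysis. Sections 10.1.5.1 and 10.1.5.2 leave the data for those reviews to charters that are not in the documents. Section 9 calls itself a summary and defers detail to a later SAP.
- **That dipstick results have no summary method.** Section 9.3.1 provides counts and percentages for categorical variables.
- **That a table of grades would reproduce the stopping count.** It would not. On a natural reading the criteria also require an at least possible relationship to study drug, and they require repeat confirmation. Grade carries neither.
- **That 6 is the denominator of the criterion.** The criterion applies to a cohort of up to 8 including placebo, and only in Period 1.

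Laboratory results recorded as AEs are also already tabulated by severity. What remains is that Section 9, which says it covers the most important endpoints, gives part of the primary endpoint no count of participants by grade, and that the grading and counting passages disagree. Deferral to the SAP means that the gap can still be closed; it does not show that it has been.

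**Conclusion.** The point holds for the final analysis. As written, that analysis cannot show how many participants in each dose group reached laboratory grade 2 or higher, or grade 3 or higher, and cannot compare those counts with pooled placebo. The gap concerns graded values not recorded as AEs. How many there will be cannot be known from the documents. With 6 active participants per dose, each one missed is about 17 percentage points.

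The conclusion rests on Section 9.3.5.2 as it stands, with no knowledge of the later SAP or the charters. It does not extend to a claim that the escalation decisions are unsupported. The inconsistencies between Section 10.2 and the stopping criteria, and between the synopsis and Section 4.1, are separate. They are plain on the page whatever the SAP adds. This is an inexpensive improvement that should be made before the SAP is finalised; it is not a defect that undermines the trial.

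**What to change.** **Analysis.** Add to Section 9.3.5.2, and carry into the SAP, a table and listing of participants by baseline grade against worst post-baseline CTCAE v5.0 laboratory grade, by analyte and dose group. Include every result that has a value-based grade, regardless of clinical significance, and show counts at grade 2 or higher and at grade 3 or higher. The listing should flag investigator-assessed relatedness and repeat confirmation where recorded, so that a reader does not take grade alone for the stopping count.

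**Reconciliation.** State which laboratory results are graded, so that Section 10.2 agrees with the confirmation requirement in the synopsis and Section 4.1. State whether the stopping criteria count participants or events, so that the synopsis agrees with Section 4.1. The sponsor decides which rule applies in each case.

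**Cost.** The analysis part needs SAP text and programming. It uses laboratory values already scheduled, with no added visits or samples. Two things should be checked, because the documents do not state them: that the database holds the reference limits where a grade depends on them, and whether relatedness is captured for laboratory values not recorded as AEs. The reconciliation needs a change to the protocol text.

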Period 1 will evaluate single ascending doses of WVE-006 in up to five cohorts of up to 8 healthy participants each. An additional cohort (Cohort 6) may be included to evaluate concentration-QTc. Each cohort will include up to 6 WVE-006-treated and up to 2 placebo-treated participants (3:1 active:placebo). Participants will receive a single subcutaneous (SC) dose of WVE-006 or placebo on Day 1.

The starting dose and dose escalation are designed based on the following considerations:

CCI

The Dose Escalation Committee (DEC) and the Data Monitoring Committee (DMC) will review available safety and PK data through Day 8 for each dose cohort in combination with all available, previously accumulated safety data, as well as available PK data from participants enrolled in the study to date, to recommend subsequent dose escalation.

A sentinel strategy will be employed for the first 2 participants (1 active:1 placebo) of every new dose level during the SAD portion of the study. The sentinel participants will be dosed and monitored in the clinic for a minimum of 48 hours to identify any potential acute safety events. If neither of these sentinel participants experiences stopping criteria and if there are no other safety concerns during this 48-hour period, the remaining 6 participants will be randomized in a blinded fashion to active study drug (n=5) or placebo (n=1) and may be dosed on the same day. These participants will be observed in clinic for 48 hours after administration of study drug. Participants will attend weekly clinic visits on Weeks 0 through 12 to be followed for safety, tolerability, and PK assessments through Day 85 per schedule of assessments (SoA).

Period 2

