
Number of Participants (Planned): Up to 48 participants are planned to be enrolled; up to 40 participants in Period 1 (8 per each of the up to five planned SAD cohorts) and up to 8 new participants in the multidose Period 2.
 
Should the DEC and DMC recommend to include an optional SAD cohort, an additional 8 participants will be enrolled for a total of up to 56 participants. Fewer than 48 participants may be enrolled if the DEC and DMC decide fewer cohorts are needed.
			

Study Arms and Duration:
 
Study arms in both Period 1 and Period 2 are up to 6 WVE-006 and up to 2 placebo treated participants (3:1 active:placebo) in each of the planned cohorts.
 
Period 1 SAD: duration for each participant is expected to be up to 16 weeks: Screening of up to 28 days, followed by a single dose administration on Day 1, followed by safety, tolerability, and PK assessment through Day 85.
 
Period 2 Multidose: duration for each participant is expected to be up to 20 weeks: Screening of up to 28 days, followed by 3 dose administrations on Weeks 0, 2, and 4, followed by safety, tolerability, and PK assessment through Day 113 Visit (i.e., Day 85 following last dose administration).
			

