	Pre-dose	Post dose												
	≤30 min prior to dose ^b	30 min (±5 min)	1 hr (±5 min)	2 hr (±5 min)	4 hr (±10 min)	6 hr (±10 min)	8 hr (±10 min)	12 hr (±10 min)	24 hr (±30 min)	36 hr (±4 hr)	48 hr (±4 hr)	(±3 days)	(±3 days)	(± 3 days)
Plasma PK ^a	X	X	X	X	X	X	X	X	X	X	X	X	X	Every week
CBC, CRP, fibrinogen, coagulation, albumin	X					X			X		X	X	X	Every week
Complement	X			X	X	X			X		X	X	X	Week 4 only
Cytokines ^c	X			X	X	X			X		X	X	X	Week 4 only

Abbreviations: CBC = complete blood count; CRP = C-reactive protein; PK = pharmacokinetic.

^a Sufficient plasma PK sample volume to cover both WVE-006 and potential metabolites. When applicable and feasible, PK blood sampling should follow evaluations of vital signs and ECGs to reduce any impact on these measurements.

^b Pre-dose laboratory results are NOT required prior to dosing.

^c Cytokine samples will be collected and may be analyzed for the following cytokines: IL-1β, IL-6, IL-10, IL-12/23 (P40), IFN-γ, TNF-α, MCP-1, and MIP-1β

Table 3 Urine PK Cumulative Collection Periods (Period 1)

Study Day/ Time Frame	Day 1					Day 2	Day 3
	0-4 hr	4-8 hr	8-12 hr	12-18 hr	18-24 hr	24-36 hr	36-48 hr
Urine PK ^a	X	X	X	X	X	X	X

Abbreviation: PK = pharmacokinetic.

^a Urine for PK assessments will be collected continuously through 48 hours per the stated time periods. For each of these time periods, total volume will be captured in the electronic case report form (eCRF).

Table 4 Triplicate ECG Assessment Time Points (Period 1)

Study Day/ Specific Time	Day 1											Day 2	Day 3
	Pre-dose			Post dose									
	-45 min ±5 min	-30 min ±5 min	-15 min ±5 min	30 min ±5 min	1 hr ±5 min	2 hr ±5 min	4hr ±10 min	6hr ±10 min	8hr ±10 min	12hr ±10 min	24hr ±30 min	48hr ±4 hr	
ECG ^a	X	X	X	X	X	X	X	X	X	X	X	X	X

Abbreviations: ECG = electrocardiogram

^a Digital ECG monitoring for at least 48 hours from Day -1 through Day 2. Additional triplicate ECG measurements at the time points listed here.**Table 5 Overall Schedule of Assessments (Period 2)**

	Screening Period ^a	Treatment Period								Follow-up Visit				ET
Visit	1	2				4	6			3, 5, 7, 8, 9, 11, 12, 13, 14, 15, 16	10	14	15	
Study Week	Week -4 to Week 0	Week 0 CRU Stay				Week 2	Week 4 CRU Stay			Week 1,3, 5, 6, 7, 9, 10, 11	Week 8	Week 12	Week 16	

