4.3 Justification for Dose

Initial Dose

As described in the International Council for Harmonization (ICH) M3(R2) guideline, the selection of the first-in-human (FIH) dose and dose escalation plan will not be higher than that supported by NOAELs from the 5-week interim data of the GLP 13-week repeat dose toxicity studies in mice and cynomolgus monkeys. Selected doses were based on the totality of the data for both mouse and cynomolgus monkey, including the NOAEL provided by the GLP toxicity studies, projected pharmacologically active dose and assessment for potential QTc prolongation risks. The initial dose was selected using the most relevant approaches described in:

- US Food and Drug Administration (USFDA) guidance for industry: [Estimating the Maximum Safe Starting Dose in Initial Clinical Trials for Therapeutics in Adult Healthy Volunteers](#) (2005).
- European Medicines Evaluation Agency (EMA) [Guideline on strategies to identify and mitigate risks for first-in-human and early clinical trials with investigational medicinal products](#) (2017)

CCI [REDACTED] Two interspecies scaling approaches were used for HED and safety margin projection, a conservative approach based on body surface area (BSA) scaling ([FDA, 2005](#)), as well as an empirical approach based on body weight supported by literature, which showed a 1:1 body-weight-based conversion factor from monkey to human and an approximately 1:7 body-weight-based conversion factor from mouse to human for plasma exposure ([Nanavati et al., 2021](#); [Wang et al., 2019](#)).

The pharmacological activities of WVE-006 are not expected in HV CCI [REDACTED]

Dose Escalation

CCI

The planned initial dose for Period 1 is 30 mg (Period 1, Cohort 1). Subsequent dose levels will be determined by the DEC and DMC based on previous Period 1 cohort data and will not exceed a CCI increase of the prior dose. The maximum dose will not exceed the limit specified in [Section 4.1.2](#). Dosing decisions will be communicated directly to the site.

CCI

If adequate safety and tolerability is observed in the initial dose cohorts (Cohorts 1 to 5) and no cohort stopping criterion was met, an optional cohort (Cohort 6) may be conducted in order to characterize the safety, tolerability, PK and the relationship between drug concentration and QTc prolongation at an appropriate dose.

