9.1 Sample Size Determination

The sample size for this Phase 1 study on HV was not calculated on the basis of statistical hypothesis testing. However, the number of participants (up to 40 in the SAD period and 8 in the multiple-dose period) is considered sufficient for this study to assess safety and tolerability for WVE-006 and to establish PK profile of WVE-006.

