PK parameters for WVE-006 and potential metabolites will be calculated using non-compartmental methods. PK parameters will be summarized for each WVE-006 dose group on the PK population using descriptive statistics: n, arithmetic mean, median, SD, minimum, maximum, and percent coefficient of variation (CV%); in addition, the geometric mean and geometric CV% will be reported for C_{max} and AUCs.

The PK parameters described in [Section 8.5](#) will be calculated for participants who receive at least one dose of WVE-006 during the study. Additional PK parameters may be evaluated if deemed necessary.

When appropriate, the correlation between QTcF and WVE-006 will be evaluated, and the results may be reported separately from the Clinical Study Report.

When appropriate, the identification and quantification of WVE-006 and its metabolites in urine will be performed and the results may be reported in a separate report.

9.3.7 *Interim Analyses*

No interim analyses are planned.

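### The concentration-QTc analysis is specified only as a correlation, which gives no QTcF change in milliseconds and leaves baseline, placebo and repeated readings unspecified

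*Combined protocol and SAP*

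**What the plan says.** The synopsis and Section 4.1 say of the optional cohort: "An additional cohort (Cohort 6) may be included to evaluate concentration-QTc". Section 4.3 is broader: the cohort is there to "characterize the safety, tolerability, PK and the relationship between drug concentration and QTc prolongation at an appropriate dose". If it is run, "an additional 8 participants will be enrolled for a total of up to 56 participants".

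The only analysis text is the sentence in Section 9.3.6: "When appropriate, the correlation between QTcF and WVE-006 will be evaluated, and the results may be reported separately from the Clinical Study Report". It does not say whether QTcF is raw or change from baseline, how placebo participants enter, how several readings from one person are handled, or what estimate and interval will be reported.

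Four other places bear on it:
- Section 3, Table 8 counts changes in QTcF within the primary safety endpoint. Concentration-QTc itself is not a listed objective or endpoint.
- Section 9.3.1 defines baseline as the last non-missing pre-dose value, pools SAD placebo participants across cohorts, and applies analyses to both periods unless stated otherwise. None of this is tied to the concentration-QTc analysis.
- Section 9.3.5.2 plans one ECG-specific summary, a Normal/Abnormal shift table by dose group.
- The opening of Section 9 leaves further detail to an SAP to be finalised before database lock. The document supplied contains no separate SAP text.

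**The concern.** The useful answer from a concentration-QTc analysis is how many milliseconds QTcF is expected to change at the concentrations reached, relative to placebo, and how large that change could plausibly be. A correlation coefficient answers neither part, however it is computed. Nothing else in Section 9 commits to that estimate: the shift table has only two categories, and the general descriptive statistics of Section 9.3.1 do not use concentration.

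The second issue is the error structure. Each participant contributes a series of readings, QTcF differs between people, and it can drift over the day. A method that treats the pairs as independent, uses raw QTcF and has no time or placebo term would overstate its precision and could mistake diurnal drift for a drug effect. Up to eight extra healthy participants may be enrolled partly for this question, so the analysis should be able to answer it.

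**Working it through.** **No plan figure to reproduce.** Section 9.1 says the sample size "was not calculated on the basis of statistical hypothesis testing", and the documents give no SD, effect size or target precision for QTcF. All SDs below are therefore assumptions, shown as ranges.

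**Counts.** 5 × 8 = 40 in Period 1; 40 + 8 = 48 with Period 2; 48 + 8 = 56 with Cohort 6. Six SAD cohorts at 6 active and 2 placebo give 36 active and 12 placebo. Table 4 has three pre-dose ECG times (-45, -30, -15 min) and nine post-dose times (0.5, 1, 2, 4, 6, 8, 12, 24, 48 h). Table 2 samples plasma at the same nine times, plus 36 h. Matched active pairs: 6 × 9 = 54 in Cohort 6 and 36 × 9 = 324 over six cohorts.

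**What a coefficient delivers.** r = slope × SD(concentration) / SD(QTcF). The same slope in ms per unit concentration gives a different r when the doses are spread differently or the participants are more alike. On raw QTcF the denominator is mostly between-person variation. The between-person share (ICC) is 144/(144+64) = 0.69 for SDs of 12 and 8 ms, 225/(225+64) = 0.78 for 15 and 8, and 225/(225+36) = 0.86 for 15 and 6.

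**Design effect, simplest case.** If exposure varied only between participants, the variance would be understated by 1 + (m - 1) × ICC with m = 9:
- ICC 0.3: 1 + 8 × 0.3 = 3.4. SE understated √3.4 = 1.8-fold; 54 pairs are worth 54/3.4 ≈ 16.
- ICC 0.8: 1 + 8 × 0.8 = 7.4. SE understated √7.4 = 2.7-fold; 54 pairs are worth 54/7.4 ≈ 7.

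**Simulation with concentration also varying within participants.** True slope zero, 1,500 trials per setting. Assumptions: the three SD pairs above, diurnal amplitude 0 or 4 ms, exposure CV about 30%, an illustrative one-compartment curve, and doses spread 10-fold. The naive analysis regresses raw QTcF on concentration over pooled pairs; its test is the same as that of the correlation. The comparator is a random-intercept model of change from baseline with concentration, treatment, time and centred baseline, and with placebo included.

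| Data used | Naive, active only | Naive, with placebo at zero | Mixed model |
|---|---|---|---|
| Cohort 6 alone (6 + 2) | 9.5-11.5% | 29-34% | 5.6-7.0% |
| Six SAD cohorts (36 + 12) | 27-32% | 31-36% | 4.9-5.9% |

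Entries are false-positive rates at a nominal 5%. Monte Carlo SE near 5% is √(0.05 × 0.95/1500) = 0.6 points.

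For the naive active-only analysis, the true SD of the slope was 1.16-1.23 times its reported SE in Cohort 6 (95% interval coverage 88-91%) and 1.81-1.92 times over six cohorts (coverage 68-73%). Mixed-model coverage was 93-95%. The 4 ms diurnal swing also biased the naive slope, by about 1 ms at peak concentration.

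**Why pool cohorts.** For a simple active-minus-placebo comparison of QTcF change at one time point, the 90% half-width is t × SD × √(1/n₁ + 1/n₂). With an assumed SD of change of 7-12 ms:
- 6 v 2 (t = 1.943, 6 df): 1.943 × 7 × 0.816 = 11.1 ms, up to 19.0 ms at SD 12.
- 6 v 12 (t = 1.746, 16 df): 1.746 × 7 × 0.5 = 6.1 ms, up to 10.5 ms at SD 12.

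Cohort 6 with only its own two placebo participants says little, so the value lies in using all SAD cohorts together.

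**The case against.** The strongest reply is that the sentence is brief rather than wrong. It does not say Pearson, raw QTcF, independent pairs or active participants only. Section 4.3 speaks of a relationship, so correlation may be loose wording for the same thing. The analysis is conditional, belongs to an optional cohort with other aims and is not a listed endpoint. Its detail is left to an SAP. The design already collects what a proper model needs. No hypothesis test is planned, so a false-positive rate describes a test nobody promised.

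Most of this stands. A reader might infer that the plan ignores baseline, placebo and repeated measures and so will report wrong error bars. The documents do not support that: they are silent on these points, and Section 9.3.1 does define a baseline and pool SAD placebo. A reader might also infer that concentration-QTc is the sole reason for Cohort 6, but Section 4.3 adds safety, tolerability and PK. Nor does QTcF change being part of the primary endpoint oblige the sponsor to put an exposure-response model in the Clinical Study Report; where it is reported is the sponsor's choice.

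The deferral does not remove the point. The protocol names a method, and an SAP that only elaborates a correlation would still give no estimate in milliseconds. The general last-non-missing rule would also use only one of the three pre-dose ECG times unless the SAP says otherwise.

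**Conclusion.** The point holds as under-specification, together with a named statistic that cannot answer the question posed. That part needs no assumptions.

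The error-bar consequence is conditional on the correlation being taken literally as a pooled analysis of raw QTcF. Its size then rests on the assumed SDs (12-15 ms between, 6-8 ms within), the illustrative concentration curve and the dose spread. Under these, the false-positive rate is about 10-36% against about 5-7% for the mixed model. The low end is Cohort 6 active participants alone; the high end is all six cohorts with placebo. The rejection rate here is a gauge of how far the reported precision would be wrong, not a claim about a planned test.

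The mixed model is not perfect in eight people: its 7.0% for Cohort 6 alone is somewhat above nominal, which is a further reason to pool cohorts.

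This is a cheap improvement, not a flaw in the design or a threat to the primary safety analysis.

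**What to change.** In Section 9.3.6 and the SAP, replace the correlation with a linear mixed-effects model:

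- **Response:** change from baseline in QTcF, with baseline the mean of the three pre-dose triplicate ECG time points.
- **Terms:** WVE-006 concentration, treatment (active/placebo), nominal time, centred baseline, and participant random effects.
- **Data:** all SAD cohorts pooled, including Cohort 6 if run, with placebo at concentration zero. State whether Period 2 data are included, since Section 9.3.1 applies analyses to both periods by default and Table 7 schedules ECGs after the first and last Period 2 doses.
- **Report:** the predicted placebo-corrected change in QTcF, which is the treatment effect plus slope × concentration, at each dose's geometric mean Cmax with a 90% CI.

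The matched PK samples, triplicate ECGs, pre-dose ECGs and placebo data are already scheduled. The cost is a paragraph of text and some extra modelling, with no added visits, samples or participants.
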